3.3 DEVIATIONS FROM PROTOCOL

Since the finalization of the Protocol v2.0, the following updates have been made to the planned analysis:

Planned Interim Analysis

The statistic used to determine futility in the planned interim analysis per Protocol v2.0 was the hazard ratio:

- If the hazard ratio seen at the interim is below the calculated futility bound, the trial may be declared futile and recruitment will be stopped.

This has been updated to the p-value, to ensure consistency between the proportional hazards and non-proportional hazards scenarios in the analysis:

- If the p-value seen at the interim is above the calculated futility bound, the trial may be declared futile and recruitment will be stopped.

Clinical Response Definition

Clinical Response is defined per protocol as:

- For patients who achieve four of the five vital sign resolution criteria, both the temperature and oxygen saturation response criteria must be maintained for 24 hours for the clinical response endpoint to be met or hospital discharge, whichever occurs first.

This has been updated to:

- Clinical response is defined as resolution of at least 4 of the 5 vital signs within the respective resolution criteria, maintained for at least 24 hours, or hospital discharge, whichever occurs first.

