NEWS2 was developed for patients aged ≥ 16 years; however, children aged 12–16 years have very similar physiological parameter ranges as adults. In this study, NEWS2 is not being used as an early warning system to identify patients who may need escalating levels of care; rather, it is being used to standardize vital sign collection which will facilitate setting severity levels for inclusion and demonstrating response to treatment. Most pediatric early warning scores are complex and designed to detect critical illness in younger children. For the purposes of this study, a patient achieving a NEWS2 of ≤ 2 is likely to represent a meaningful degree of clinical improvement (i.e., clinically stable and potentially eligible for discharge). Importantly as well, the method of statistical analysis and the selection of a clinically meaningful difference between treatment groups are possible for an endpoint of this design.

The *first* key secondary endpoint will be the proportion of patients per category in the 6-point ordinal scale at Day 7. The categories within this scale (see Section 4.5.16) reflect the clinical status of patients during their hospital stay. The clinical status should be assessed to reflect the most accurate condition of the patient from a medical perspective, to minimize the effects of administrative or non-medical factors (e.g., the hospital bed availability may lead to patients not being cared for in the ward most suitable for their condition). This endpoint has received considerable interest for use in this patient population. There is as yet no definition of a minimum clinically relevant difference between treatment groups; however, the 6-point ordinal scale will be used in

this study to investigate the change in clinical state of patients as the key secondary endpoint.

The second of the two key secondary endpoints will be “time to clinical response”. This endpoint is defined by the time to hospital discharge or the time to vital sign parameter stabilization. Vital sign stabilization is based on achieving a set temperature, combined with achieving a set oxygen saturation, plus two out of three other parameters related to respiratory status, blood pressure or heart rate (see Section 6.5).

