6.4.2 Key Secondary Endpoints

6.4.2.1 *6-Point Ordinal Scale Measured at Day 7*

For the key secondary endpoint of 6-point ordinal scale the response rate of the scale will be measured at Day 7. The 6-point ordinal scale will be analyzed using the Cochran-Mantel-Haenszel test statistic stratified by region (i.e., North America, EMEA, ROW), NEWS2 (≤ 7 , > 7), and time from symptom onset to study treatment (≤ 48 hours, > 48 hours).

For the ordinal endpoint, missing data will be imputed by using the patient's last non-missing score for any patient with a missing response at Day 7. If the patient died

prior to Day 7, the patient will be included in the death category. The proportion of patients with a response in each category will be summarized by treatment group and Cochran-Mantel-Haenszel test statistic result presented.

A sensitivity analysis will be conducted where missing scores at Day 7 will be replaced by the patient's last non-missing score +1 (*i.e.*, *one ordinal category worse*). If the patient died prior to or on Day 7, the patient will be included in the death category.

6.4.2.2 *Time to Clinical Response*

The additional key secondary endpoint of the "time to clinical response" will be based upon hospital discharge, fever, and oxygen saturation, and two or more of the following: improved respiratory status, heart rate, or systolic blood pressure. The exact criteria for each parameter are as follows:

Temperature:^a

- $\leq 36.6^{\circ}\text{C}$ ($\leq 97.9^{\circ}\text{F}$)—axillary, or
- $\leq 37.2^{\circ}\text{C}$ ($\leq 99^{\circ}\text{F}$)—oral, or
- $\leq 37.7^{\circ}\text{C}$ ($\leq 99.9^{\circ}\text{F}$)—rectal, core, or tympanic

AND

Oxygen Saturation:^{b,c}

- $\geq 95\%$ (without supplemental oxygen)

AND two of the following three:

Respiratory Status:

- Return to pre-morbid oxygen requirement (patients with chronic oxygen use), OR
- Need for supplemental oxygen (given in any way—ventilator, non-invasive ventilation, facemask, face-tent, or nasal cannula) to no need for supplemental oxygen, OR
- Respiratory rate ≤ 24 per min (without supplemental oxygen)

Heart Rate:

- ≤ 100 beats per min

Systolic blood pressure:^d

- ≥ 90 mmHg
- OR

Hospital Discharge

- a Without the use of antipyretics within 8 hours.

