- b A patient with a history of chronic hypoxia (without supplemental oxygen) will satisfy the normalization criteria for oxygen saturation if the value (without supplemental oxygen) is $\leq 2\%$ from the patient's historical oxygen saturation before enrollment as documented in the patient's medical records, if available
- c This requirement is waived for patients with a history of chronic supplemental oxygen requirement who have an oxygen saturation $< 95\%$ with supplemental oxygen documented in the patients' medical records within 12 months of enrollment.
- d Without inotropic support given within 2 hours of assessment.

For patients who achieve four of the five vital sign resolution criteria above, both the temperature and oxygen saturation response criteria must be maintained for 24 hours for the clinical response endpoint to be met.

Time to clinical response will be analyzed using *similar* methods and sensitivity analyses as specified for the primary endpoint. Patients who are lost to follow-up, who do not have a clinical response, or who die will be censored at their last contact date or date of death, whichever is applicable. *Further details on methods and missing data rules will be fully detailed in the SAP.*

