4.5.2.3 Time to Clinical Response

Time to clinical response will be based upon hospital discharge, fever, and oxygen saturation, and two or more of the following: improved respiratory status, heart rate, or systolic blood pressure ([Marty et al. 2017](#)). Time to clinical response is defined as the time from start of study treatment until the timepoint where "clinical response", as defined below, is met.

Patient should meet conditions A and B, and (2 of C, D and E) OR F below. For patients who achieve four of the five vital sign resolution criteria above each of these must be maintained for 24 hours for the clinical response endpoint to be met. As for the primary endpoint, missing data will not be imputed.

A. Temperature

$\leq 38.6^{\circ}\text{C}$ ($\leq 102^{\circ}\text{F}$) if axillary, or

$\leq 37.2^{\circ}\text{C}$ ($\leq 99^{\circ}\text{F}$) if oral, or

$\leq 37.7^{\circ}\text{C}$ ($\leq 100^{\circ}\text{F}$) if rectal, core, temporal or tympanic

- without use of antipyretics within 8 hours (missing antipyretics will be assumed to have been taken)

B. Oxygen Saturation

$\geq 95\%$ (without supplemental oxygen)*+

*This requirement will be waived for patients with a history of chronic supplemental oxygen requirement who had a baseline oxygen saturation $< 95\%$ with supplemental oxygen, within 12 months of enrolment as documented in the patient's medical records.

+A patient with a history of chronic hypoxia (without supplemental oxygen) can satisfy the normalisation criteria for oxygen saturation if the value (without supplemental oxygen) was $\leq 2\%$ from patient's historical oxygen saturation baseline as recorded within 12 months before enrolment and documented in the patient's medical records.

C Respiratory Status:

- I. Return to pre-morbid oxygen requirement (patients with chronic oxygen use), OR
- II. Need for supplemental oxygen (given in any way—ventilator, non-invasive ventilation, facemask, face-tent, or nasal cannula) to no need for supplemental oxygen, OR
- III. Respiratory rate ≤ 24 per min (without supplemental oxygen)

D Heart Rate

≤ 100 beats per min

E Systolic blood pressure

≥ 90 mmHg, without inotropic support given within 2 hours of assessment

OR

F Hospital Discharge

TTCR is calculated as per [Table 6](#).

Table 6 TTCR Calculation

TTCR based on	TTCR (hours)

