Event	Censor	Date and Time
Clinical Response (based on vital signs assessments)	No	first vital signs assessment where 4 out of 5 criteria initially met and subsequently maintained for 24 hours period
Clinical Response (based on vital signs criteria met prior to discharge)	No	first vital signs assessment where 4 out of 5 criteria initially met and maintained prior to discharge
Clinical Response (based on hospital discharge)		
- hospital discharge to another hospital (i.e. hospital admission within 24 hours) and discontinue study on same day	Yes	hospital discharge
- hospital discharge to another hospital (i.e. hospital admission within 24 hours) and continue study	Yes	hospital discharge
- hospital discharge against medical advice	Yes	hospital discharge
- all other hospital discharge	No	hospital discharge
Death prior to achieving a clinical response	Yes	last vital signs assessment prior to death
Discontinuation for any reason prior to achieving a clinical response	Yes	last vital signs assessment prior to discontinuation
Lost to follow-up	Yes	last vital signs assessment
No clinical response	Yes	last vital signs assessment

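### The SAP gives two conflicting responder definitions for time to clinical response: Section 3.3 and Table 7 read literally as any four of five vital signs, while Section 4.5.2.3 and the protocol make temperature and oxygen saturation mandatory

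*SAP*

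**What the plan says.** The protocol makes two components compulsory. Section 3.3.4 explains the endpoint this way: "Vital sign stabilization is based on achieving a set temperature, combined with achieving a set oxygen saturation, plus two out of three other parameters". Section 6.4.2.2 joins temperature and oxygen saturation with AND, and then adds "AND two of the following three", meaning respiratory status, heart rate and systolic blood pressure. Hospital discharge is the alternative route. A separate sentence sets the duration rule for patients who achieve four of the five criteria: "both the temperature and oxygen saturation response criteria must be maintained for 24 hours".

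SAP Section 3.3 lists changes made since protocol version 2. It presents that duration sentence as the protocol's definition of clinical response and puts this in its place: "Clinical response is defined as resolution of at least 4 of the 5 vital signs within the respective resolution criteria". The state must persist for 24 hours or more, and an earlier discharge also counts. Neither temperature nor saturation is named.

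SAP Section 4.5.2.3 labels the criteria A (temperature), B (oxygen saturation), C (respiratory status), D (heart rate), E (systolic pressure) and F (discharge), and states: "Patient should meet conditions A and B, and (2 of C, D and E) OR F below". Its duration rule is that "each of these must be maintained for 24 hours for the clinical response endpoint to be met". The first column of Table 6 keeps A and B compulsory. The date-time column of the same rows refers to four out of five criteria. Table 7, which fixes the event time, says: "first vital signs assessment where 4 out of 5 criteria initially met and subsequently maintained for 24 hours period".

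**The concern.** A confirmatory endpoint needs one responder definition, fixed in advance. This one was raised to key secondary status at a regulator's request and stands third in the fixed testing sequence, after TTCI and the Day 7 ordinal scale. The SAP gives no rule for which section prevails. Section 3.3 carries weight because it is the formal record of departures from the protocol.

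If Section 3.3 or Table 7 were programmed as written, a patient who stayed febrile, or who stayed below the saturation limit, could count as a responder by the vital-sign route. Fever and hypoxia would no longer be necessary conditions for non-response. The event time could also move, because the clock could stop when any four criteria were first met rather than when temperature and saturation were among them.

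The antipyretic rule would lose much of its purpose too. Section 4.5.2.3 fails criterion A if antipyretics were used within 8 hours, and counts missing antipyretic data as use. Under any four of five, a patient meeting B to E would respond regardless of antipyretics.

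**Working it through.** The plan states no figure on this point to reproduce. The check compares the two rules over every possible combination of criteria.

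**Inputs.** Five criteria, each met or unmet: A to E as labelled in SAP Section 4.5.2.3. Discharge (F) is common to both rules and is left out.

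**Rules.**
- Rule 1 (Section 3.3 and Table 7, read literally): A + B + C + D + E ≥ 4.
- Rule 2 (Section 4.5.2.3, Table 6 first column, protocol 6.4.2.2): A = 1, B = 1 and C + D + E ≥ 2.

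**Counts among the 2^5 = 32 patterns.**
- Rule 1: exactly four met (5 patterns) plus all five met (1 pattern) = 6.
- Rule 2: exactly two of C, D, E met (3 patterns) plus all three met (1 pattern) = 4.
- Difference: 6 − 4 = 2. Every pattern that passes Rule 2 also passes Rule 1.

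| Unmet criterion | Rule 1 | Rule 2 |
|---|---|---|
| None | responds | responds |
| C only | responds | responds |
| D only | responds | responds |
| E only | responds | responds |
| A only (temperature) | responds | does not respond |
| B only (saturation) | responds | does not respond |

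**Illustrations (hypothetical, each state sustained for 24 hours).**
- Temperature 39.5 °C, SpO2 96% on air, respiratory rate 20, heart rate 98, systolic pressure 120: only A is unmet.
- Afebrile, SpO2 88% off oxygen, respiratory rate 22, heart rate 95, systolic pressure 110, no history of chronic hypoxia or chronic oxygen use: only B is unmet.

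Both respond under Rule 1 and neither does under Rule 2.

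**Event time (hypothetical).** B to E are met from hour 20, A from hour 40, and all then hold. Under Rule 2 the response is at hour 40. Taken literally, the date-time wording in Tables 6 and 7 gives hour 20. The gap is 40 − 20 = 20 hours, in a patient who responds under both rules.

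**What Section 3.3 set out to change.** The protocol sentence it replaces says that "both the temperature and oxygen saturation response criteria must be maintained for 24 hours for the clinical response endpoint to be met". That sentence governs which criteria must persist. The AND structure of protocol 6.4.2.2 is not listed as changed. Section 4.5.2.3 extends the 24-hour requirement to every criterion met and leaves A and B compulsory.

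**The case against.** The strongest reply is that Section 4.5.2.3 is where the SAP defines the endpoint. It says response is as defined there, and it keeps A and B. A footnote to SAP Table 1 also points to protocol Section 6.4.2 for the criteria. In Table 6 the four-out-of-five phrase sits in rows labelled with the A-and-B rule, so there it looks like shorthand. The shorthand comes from the protocol, which speaks of four of five criteria directly after a list making temperature and saturation compulsory. On duration, the SAP is stricter than the protocol. The endpoint is formally tested only if the first two in the sequence succeed, and the primary endpoint is untouched.

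Most of this stands. A reader might infer from Section 3.3 that the sponsor has dropped the mandatory pair, so that a febrile or hypoxic patient now counts as a responder. The documents do not support that. The section specifying the analysis says the opposite, and the sentence being replaced concerns duration.

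What the reply does not remove is the contradiction. No text says that four out of five is shorthand. Table 7 uses it without repeating A and B, and Section 3.3 offers it as the definition.

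**Conclusion.** The SAP states two different responder rules for one key secondary endpoint in the controlled testing sequence. Read literally, Section 3.3 and Table 7 accept exactly two patterns that Section 4.5.2.3 and the protocol reject: temperature alone unmet and oxygen saturation alone unmet, each with the other four criteria sustained for 24 hours. The four-out-of-five wording in Tables 6 and 7 could also date responses earlier.

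The pattern count is exact but is not an effect size. The documents do not show how many patients would fall into the two extra patterns, or how far event times or the treatment comparison would move. A programmer who followed Section 4.5.2.3 alone would apply the compulsory pair. That Section 3.3 meant only to lengthen the duration rule is an inference from the sentence it replaces and from how Section 4.5.2.3 carries the change. Responses without a saturation of 95%, through discharge or the chronic hypoxia and chronic oxygen provisions, are in the protocol as well and are not part of this conflict.

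Severity is moderate. This is an internal contradiction to reconcile, not a demonstrated weakening of the endpoint.

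**What to change.** Before unblinding:

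- In SAP Section 3.3, define clinical response as meeting the temperature AND oxygen-saturation criteria AND at least two of respiratory status, heart rate and systolic blood pressure, all maintained for at least 24 hours, or discharge from hospital if that comes first. Say that the only change from the protocol is that the 24-hour requirement now covers all the criteria met.
- In the date-time column of Table 6 and the two vital-sign event rows of Table 7, replace the four-out-of-five wording with the lettered rule from the first column of Table 6.

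This matches Section 4.5.2.3 and the structure in protocol Section 6.4.2.2. It costs a few lines of SAP text and no new data. The downside is that response may be reached later than under the looser reading.

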4. STATISTICAL METHODS

4.1 ANALYSIS POPULATIONS

4.1.1 ITT Population

The intent-to-treat (ITT) population is defined as all randomized patients, whether or not the patient received the assigned treatment. The ITT patients will be analyzed according to the treatment assigned at randomization.

4.1.2 Modified Intent-to-Treat Infected Population

Efficacy analyses will be conducted for the mITTI population. This is defined as all patients randomized who received at least one dose of study drug and were centrally assessed as RT-PCR positive for influenza at any timepoint, with patients grouped according to the treatment assigned at randomization.

4.1.3 Pharmacokinetic Population

The PK population will consist of patients who received any amount of study treatment and who provided at least one measurable post-dose concentration at a scheduled visit

timepoint. Patients may be excluded from the PK population only if they significantly violate the inclusion or exclusion criteria, deviate significantly from the protocol, or if data are unavailable or incomplete. Decisions on patient exclusion from the PK population will be made prior to database closure by the clinical pharmacologist. Excluded patients will be documented, together with the reason for exclusion.

4.1.4 Sparse Pharmacokinetic Population

The sparse PK population comprises all patients in the PK population who did not provide informed consent to intensive PK sampling. Decisions on patient exclusion from the sparse PK population will be made prior to database closure by the clinical pharmacologist. Excluded patients will be documented, together with the reason for exclusion. Patients with a dose modification during the course of the treatment will be fully documented but will not be excluded from the population PK analysis.

4.1.5 Extensive Pharmacokinetic Population

The extensive PK population comprises all patients in the PK population who provided informed consent to intensive PK sampling.

4.1.6 Safety Population

The safety population is defined as patients who received any amount of study treatment. Patients will be analyzed according to the treatment received. Patients who were randomized to the study but who did not receive any study drug will not be included in the safety population.

4.2 ANALYSIS OF STUDY CONDUCT

The number of patients who are randomized (ITT population), who are RT-PCR positive, who are treated (safety population), who are included in the mITT population and who discontinue or complete the study will be summarized by treatment group. Reasons for premature study withdrawal from treatment and from study will be both summarized.

Major protocol deviations will be listed and evaluated for their potential effects on the interpretation of study results.

4.3 ANALYSIS OF TREATMENT GROUP COMPARABILITY

To descriptively assess the comparability of treatment arms at baseline, summary tables will be produced for both the safety and mITTI population for clinically important baseline demographics and disease characteristics by treatment group.

These summary tables will include number of patients, mean, standard deviation, median, minimum, maximum, first and third quartiles (Q1 and Q3) for continuous demographic/disease characteristics and number and percentage of patients for categorical characteristics.

Demographic and baseline disease characteristics will be summarized as described in the following sections.

4.3.1 Baseline stratification factors

Baseline stratification factors as recorded in the IxRS will be presented as follows:

- NEWS2 (≤ 7 , >7)
- Time from symptom onset to study treatment (≤ 48 hours, >48 hours)
- Regions (i.e., North America; EMEA; and ROW)

4.3.2 Demographics

Frequency tabulations for:

- Age:
 - (<65 , ≥ 65 years)
 - (<80 , ≥ 80 years)
- Sex (male, female)
- Ethnicity (Hispanic or Latino, Not Hispanic or Latino)
 - Race (American Indian or Alaska Native, Asian, Black or African American, Native Hawaiian or Other Pacific Islander, White, Unknown)
 - Region (North America; EMEA; and ROW)
 - Female fertility status (Childbearing Potential, Surgically Sterile, Post-menopausal, Pre-menarchal)
 - Tobacco use history (never, current, previous)
 - Alcohol use history (never, current, previous)
 - Current substance use (yes, no)

will be presented by treatment group.

Descriptive statistics for age and weight will be presented.

4.3.3 Disease Characteristics and Influenza History

- RT-PCR status (positive, negative)
- Influenza Subtype
- Time from symptom onset to study treatment
- Reason for hospitalization (Current Influenza Episode or Other (Prolonged Hospitalization))
- Seriousness criteria:
 - Required ventilation or supplemental oxygen to support respiration at baseline
 - Complication requiring hospitalization

- Complication by body system category (Cardiac, Central Nervous System [CNS], Hepatic, Renal, Respiratory, Gastrointestinal, Metabolic, Musculoskeletal, Other)
- NEWS2 at baseline
- intensive care unit (ICU) status at baseline
- Chronic Hypoxia History (Yes, No, Unknown)
- Co-infections (identified via the non-influenza respiratory bacterial and virus co-infection panel)
- Previous anti-influenza treatments
 - Vaccination history (within last 6 months, within last 12 months)
 - Antiviral treatment within 48 hours prior to screening. Type of antiviral treatment utilized will be presented e.g: Oseltamivir/oseltamivir phosphate, peramivir, zanamivir, Laninamivir, Arbidol, Favipiravir, Amantadine, Rimantadine,
- Ordinal scale at Day 1 (categories 1 – 6, see Section 4.5.2.1)

Medical history data, including surgery and procedures and ongoing baseline conditions will be summarized descriptively by treatment group using the safety population. Additionally, ongoing baseline conditions present in >5% of patients in any treatment arm will be presented. Descriptive summaries of any previous and concomitant treatment will be produced by treatment group for the safety population.

